9.2 Operational definitions for (S)AEs

The occurrence of AEs will be assessed by non-directive questioning of the subject at each visit. Additionally, AEs volunteered by the subject during or between visits or detected through observation, physical examination, laboratory test or other assessments will be documented. Subjects will be instructed that they must immediately report any AEs, subjective complaints or objective changes in their well-being to the Investigator or the clinic personnel, regardless of the perceived relationship between event and test product.

All AEs must be fully recorded throughout the entire study period (from Screening Visit to Day 85) and will be entered into the subjects' eCRF, whether or not they are considered to be drug-related. Each AE should be described in detail: onset time and date, offset time and date, description of event, severity, relationship, action taken and outcome. From Day 85 and Day 225 only SAEs and AESIs will be collected.

Adverse events should be followed until recovery to the normal state has been achieved. In the event of a subject not returning to the clinical unit, every attempt will be made to contact the subject up to Day 85 after which the outcome of this event will be recorded as lost at follow-up.

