#### 12.6.1 Adverse Events

Adverse events will be coded using Version 20.0 or newer of MedDRA.

Treatment-emergent adverse events (TEAEs) are those which first occur or increase in severity or relationship probability to investigational product after the first dose of investigational product through 30 days after last dose of investigational product. Note that SAEs and AESIs are collected through 6 months after last dose of investigational product; therefore, all SAEs and AESIs will be summarized, not just treatment-emergent events.

All AEs which change in severity or relationship to investigational product are assigned a new start date and captured as a new record.

If more than 1 AE with the same preferred term is reported before the date of the dose of investigational product, then the AE with the greatest severity will be used as the benchmark for comparison to the AEs occurring during the study under the preferred term.

An overall summary of TEAEs, including the number and percentage of subjects who experience, and absolute count of treatment-emergent events for:

- Any TEAE
- Any TEAE by maximum severity
- Any TEAE considered possibly related to investigational product (defined as CRF response of "Reasonable Possibility")
- Any TEAE considered possibly related to investigational product by maximum severity
- Any SAEs
- Any SAEs considered possibly related to investigational product
- Any AEs with outcome of death
- Any AESIs (Hepatic flares and autoimmune conditions)
- Any TEAE leading to discontinuation of investigational product

The number and percentage of subjects reporting TEAEs, SAEs, or AESIs will be tabulated in the following ways by treatment group.

- By SOC and preferred term (including absolute count of events).
- By SOC, preferred term and maximum severity.
- By SOC and preferred term for TEAEs possibly related to investigational product in the opinion of the investigator (including absolute count of events).
- By SOC and preferred term for SAEs (including absolute count of events).
- By SOC and preferred term for possibly related SAEs (including absolute count of events).
- By SOC and preferred term for TEAEs leading to discontinuation of investigational product (including absolute count of events).
- By SOC and preferred term for AEs with fatal outcome (including absolute count of events).
- By SOC and preferred term for AESIs (including absolute count of events).

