##### 14.2.1.3 Missing day only

- If the month and year of the incomplete start date are the same as the month and year of the date of the first dose of investigational product, then the day of the date of the first dose of investigational product will be assigned to the missing day.
- If either the year is before the year of the date of the first dose of investigational product or if both years are the same but the month is before the month of the date of the first dose of investigational product, then the last day of the month will be assigned to the missing day.
- If either the year is after the year of the date of the first dose of investigational product or if both years are the same but the month is after the month of the date of the first dose of investigational product, then the first day of the month will be assigned to the missing day.

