#### 14.2.3 Incomplete Start Time

If the start time is missing then if the start date (or imputed start date) is the same as the date of dose, then set to the time of dose. Otherwise, set missing start times to 00:00.

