#### 14.3.1 Incomplete Start Date and time

Follow same rules as in [section 14.2.1](#) and [section 14.2.3](#).

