#### **14.4 Missing Severity Assessment for Adverse Events**

If severity is missing for an AE starting prior to the date of the dose of investigational product, then a severity of "Mild" will be assigned. If the severity is missing for an AE starting on or after the date of first dose of investigational product, then a severity of "Severe" will be assigned. The imputed values for severity assessment will be used for incidence summaries, while the actual values will be used in data listings.

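### SAE and AESI tables have no first-dose lower bound, and untimed AEs on the first-dose day tie with the dose and fall outside the TEAE definition as written

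*SAP*

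**What the plan says.** **TEAE window.** SAP 12.6.1 defines TEAEs as AEs that first occur, or increase in severity or relationship, "after the first dose of investigational product through 30 days after last dose of investigational product".

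**SAEs and AESIs.** The same section notes that these are collected for six months after the last dose and concludes that "all SAEs and AESIs will be summarized, not just treatment-emergent events". No onset condition replaces the one removed. In SAP Appendix 1, the tables of SAEs (14.3.2.4), possibly related SAEs (14.3.2.6) and AESIs (14.3.2.10) are limited only by the Safety Analysis Set.

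**Start of collection.** Protocol 9.2 states: "All AEs must be fully recorded throughout the entire study period (from Screening Visit to Day 85"). Protocol 9.2.3 has a causality category expected to apply mainly to AEs recorded before any study product is given, so pre-dose records are foreseen.

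**Missing relationship.** SAP 14.5 assigns possible relatedness to any AE with a missing assessment and does not distinguish pre-dose from post-dose events. The imputed value is used in the incidence summaries.

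**Missing onset date or time.** SAP 14.3.1 sends AEs to the medication rules: "Follow same rules as in" sections 14.2.1 and 14.2.3. If the month and year match those of the first dose, "then the day of the date of the first dose of investigational product will be assigned to the missing day". Section 14.2.1.2 does the same when only the year is known and it matches. If the start time is missing and the start date "is the same as the date of dose, then set to the time of dose". For all other dates: "Otherwise, set missing start times to 00:00".

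**The concern.** Two boundary rules in the primary safety tables do not do what they appear meant to do.

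The SAE and AESI tables are meant to reach beyond the TEAE window at its late end. By removing the whole window, the SAP also opens the early end. Events between screening and the first injection, in subjects who go on to be dosed, are then reported under the arm they were later assigned to.

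The imputation rule places an AE of uncertain onset at the moment of dosing, presumably so that it counts as on-treatment. The definition it feeds into requires onset after dosing and says nothing about ties. A programmer who codes the definition as written excludes exactly the events the imputation was meant to keep.

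With about 10 subjects per arm in a first-in-man study, and serious or special-interest events likely to be few, one record in the wrong place can change how an arm reads.

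**Working it through.** The plan gives no figure to reproduce, so the check applies its rules to example records.

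**1. TEAE boundary.** Inputs: doses on Days 1, 29 and 57 (SAP 6.0); an illustrative dose time of 10:00; imputation under SAP 14.2.1 and 14.2.3; TEAE upper limit at last dose + 30 days = Day 57 + 30 = Day 87. Each record is classified with onset strictly later than first dose (the literal text) and with onset at or later than first dose.

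| AE record | Imputed onset | TEAE if onset > first dose | TEAE if onset ≥ first dose |
|---|---|---|---|
| Five days before dosing, no time | that day, 00:00 | no | no |
| Day 1, no time | Day 1, 10:00 | **no** | **yes** |
| Day missing, month and year of first dose, no time | Day 1, 10:00 | **no** | **yes** |
| Day and month missing, year of first dose, no time | Day 1, 10:00 | **no** | **yes** |
| Day 2, no time | Day 2, 00:00 | yes | yes |
| Day 29 or Day 57, no time | 10:00 or 00:00 | yes | yes |
| Day 85 | Day 85 | yes | yes |
| Day 88 | Day 88 | no | no |

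The Day 29 and Day 57 rows show two times because the date of dose in 14.2.3 could mean any dose or only the first. The classification is the same either way. Only the three first-dose-day records change.

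**2. Why the tie arises.** SAP 12.3.2 starts the concomitant-medication window at the date and time of the first dose, inclusive. An imputed tie therefore lands inside that window. SAP 14.3.1 carries the rule to AEs, where the window opens after the dose.

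**3. SAE and AESI tables.** A subject has an SAE between screening and Day 1 and is then dosed.

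- Safety Analysis Set: the subject is a member, having received an injection (SAP 9.2).
- TEAE: no, because onset precedes the first dose.
- SAE table: yes, because treatment emergence is not required.
- Related-SAE table: yes if relationship is missing (SAP 14.5).

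**4. Does the stated reason need the lower bound removed?** The primary analysis cuts each subject's data at Day 85 (SAP 10.2). On the nominal schedule the TEAE window runs to Day 87, so for a fully dosed subject every post-dose SAE up to the cut already falls inside it. For such subjects, dropping the restriction at the primary analysis adds only pre-dose events. At the Day 225 analysis the later upper bound is needed, but the lower bound is still not in the way. For a subject who stops dosing early the TEAE window closes sooner, and the exemption does add post-dose events at Day 85.

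**5. Size.** One subject in an arm of 10 is 1/10 = 10 percentage points. This is a maximum, since it applies only if the subject has no other event in that row.

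**The case against.** The best reply on TEAEs is that nobody would code it that way. Setting onset to the dose time makes sense only if ties count as on-treatment, the medication window is inclusive, and 12.6.1 itself places its pre-treatment comparison before the date of dose. That is a fair reading of intent, but the SAP does not state it. What stands is that the loss depends on reading the boundary strictly. The number affected may also be small, because Protocol 9.2 requires onset date and time for every AE.

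On SAEs and AESIs, only dosed subjects enter the tables. Transaminase limits and the exclusion of autoimmune conditions (Protocol 6.1 and 6.2), with eligibility reviewed again at Visit 1, make a pre-dose hepatic flare or autoimmune event unlikely in anyone dosed. This makes such events rare. It does not supply the missing bound, and an unrelated SAE need not bar entry.

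Four stronger readings are tempting and not supported:

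- *Day 1 reactogenicity is lost.* Solicited local reactions are tabulated from investigator and diary assessments without a TEAE filter (SAP 12.6.2). Only untimed unsolicited AEs are exposed, including any site reaction also entered as an AE, and all of them stay in the listings.
- *SAP 14.4 contradicts 12.6.1.* Its wording, "for an AE starting on or after the date of first dose of investigational product", governs the imputation of missing severity by date. It is not a rival definition of treatment emergence.
- *Fatal-event tables are inflated.* A Safety Analysis Set member was alive at dosing. The case would need an event that began before dosing, dosing despite it, and later death from it.
- *A share of tabulated SAEs can be worked out from days of screening against days of follow-up.* That assumes an equal event rate before and after dosing and a full-length screening period. The documents give no SAE rate, and dosed subjects have passed screening.

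**Conclusion.** The point holds in two limited parts.

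The SAE and AESI part is the firmer. It follows from the stated rule with no special reading: pre-dose events in dosed subjects are tabulated by arm, and as possibly related when relationship is missing, while the reason given justifies only a later upper bound.

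The TEAE part is an unstated tie rule. It affects unsolicited AEs dated or imputed to the first-dose day with no start time, and only if the boundary is applied literally.

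The effect is at most 10 percentage points per misclassified subject in an arm of 10. How many subjects would be affected cannot be estimated from the documents. The analysis is descriptive with no hypothesis tests (SAP 12.0), so this is a minor correction, worth making because it bears on the primary safety tables.

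**What to change.** In SAP 12.6.1:

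1. Define treatment-emergent onset or worsening as at or after the date and time of first dose, and state that an event imputed to the dose time counts. This is the cautious direction: it may admit a few untimed events that truly began before the injection.
2. Restrict the SAE and AESI tables, and the matching rows of the overall AE summary, to onset or worsening at or after first dose, through Day 85 for the primary analysis and through the Day 225 visit for the follow-up analysis. Worsening needs no new derivation, because 12.6.1 already gives a changed AE a new record and start date.
3. List pre-dose SAEs and AESIs separately, or flag them in the existing listings. Once they are out of the tables, the relationship imputation in 14.5 can no longer place them among related SAEs.

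The cost is a few sentences and a small programming condition, with no new data and no protocol amendment (Protocol 10.3). SAP 4.0 allows changes up to the final version, which is issued after the blinded data review and before database lock.

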9.2.3.2 Outcome

Outcome will be defined as:

- Resolved;
- Ongoing;
- Lost to follow up.

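### SAP 12.6.1 splits one continuing adverse event into several records and counts events with no rule to rejoin them, so one episode can be counted several times

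*SAP*

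**What the plan says.** **Recording.** SAP 12.6.1: "All AEs which change in severity or relationship to investigational product are assigned a new start date and captured as a new record". The rule covers changes in either direction.

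**Treatment-emergent status.** Also in SAP 12.6.1, TEAEs are AEs which "first occur or increase in severity or relationship probability to investigational product after the first dose of investigational product", up to 30 days after the last dose. Decreases are not mentioned. SAEs and AESIs are collected for six months after the last dose, and all of them are summarised whether or not they are treatment-emergent.

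**Counting.** The overall summary gives subject numbers and percentages "and absolute count of treatment-emergent events for" each listed category, including categories by maximum severity. The SOC and preferred-term tables are introduced in terms of subjects: "The number and percentage of subjects reporting TEAEs, SAEs, or AESIs will be tabulated in the following ways by treatment group". Seven of the eight then add an absolute count of events. The exception is the table by maximum severity.

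**Outcome.** Protocol 9.2.3.2: "Outcome will be defined as" one of three values, namely resolved, ongoing or lost to follow up. SAP 12.6.1 nevertheless plans a row for "Any AEs with outcome of death" and a fatal-outcome table and listing (Appendix 1, Table 14.3.2.9 and Listing 16.2.7.5). Protocol 10.9.2 plans a table of fatal events.

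**The concern.** An event count is useful only if one clinical episode gives one event. Here the data-capture rule creates a new record at every change, and the analysis section counts events without saying what an event is. Neither SAP 12.6.1 nor the missing-data rules in SAP 14.3 to 14.5 link or collapse records.

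Safety is the primary objective, and SAP 10.2 says the primary analysis is needed to confirm formulation and dose. With about 10 subjects per arm, a few surplus records visibly change a count. The exposure is greatest for SAEs and AESIs: one hepatic flare whose severity rises and falls could appear as several AESI events. Protocol 10.9.2 also asks for AE duration, and new start dates on split records would shorten it unless it is computed over the whole episode.

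The outcome list is a separate and smaller matter. The field as defined in the protocol has no value that would feed the planned fatal-outcome outputs.

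**Working it through.** The documents give no AE rate and no rate of severity or relationship change, so there is no plan figure to reproduce. The check applies the written rules to single episodes and then shows an illustration with assumed inputs.

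**1. One episode starting after the first dose: mild, moderate, severe, moderate, mild.**
- Changes: 4. Records: 1 + 4 = 5.
- TEAE count if only first occurrence and increases qualify: 1 + 2 = 3.
- TEAE count if step-down records also qualify: 5. The SAP does not settle this. Its only benchmark rule compares on-study AEs with AEs of the same preferred term reported before dosing. An episode that began after dosing has no such benchmark, so a programmer could flag every one of its records.
- Count if the episode is an SAE or AESI: 5, because no treatment-emergent filter applies.
- Subjects: 1 in every case.

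**2. A mild AE present before dosing that becomes moderate afterwards.** There are two records: the first is not treatment-emergent, the second is. If the linked episode were dated from its first onset, it would fall before dosing and drop out of the TEAE tables. A linking rule must therefore date it from the first treatment-emergent record.

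**3. Illustration across two arms.** Records = E × (1 + q × k), where E is the number of true episodes, q the share that change severity or relationship, and k the changes per changing episode. All are assumptions: E = 10 in one arm and 30 in the other (true ratio 3.0), with k = 1 or 2.

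| q, smaller-E arm | q, larger-E arm | Records, k = 1 | Ratio | Records, k = 2 | Ratio |
|---|---|---|---|---|---|
| 0.10 | 0.10 | 11 vs 33 | 3.0 | 12 vs 36 | 3.0 |
| 0.50 | 0.50 | 15 vs 45 | 3.0 | 20 vs 60 | 3.0 |
| 0.10 | 0.25 | 11 vs 37.5 | 3.41 | 12 vs 45 | 3.75 |
| 0.10 | 0.50 | 11 vs 45 | 4.09 | 12 vs 60 | 5.0 |
| 0.25 | 0.10 | 12.5 vs 33 | 2.64 | 15 vs 36 | 2.40 |

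For example, 30 × (1 + 0.25 × 2) = 45 and 10 × (1 + 0.10 × 2) = 12, a ratio of 3.75. With equal q both arms are inflated by the same proportion (10% to 100% in the rows shown) and the ratio does not move. With unequal q it can move either way. After linking, each count returns to E. Subject counts are the same in every row.

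**4. Outcome list against planned outputs.** Protocol 9.2.3.2 offers three values, none of them fatal. Protocol 10.9.2, SAP 12.6.1 and SAP Appendix 1 all plan fatal-outcome outputs. Death does appear elsewhere: as a seriousness criterion (Protocol 9.1, Table 7), as an SAE (Protocol 9.5), and through the separate SAE form (Protocol 9.3). No text says which field feeds the fatal tables.

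**The case against.** The strongest reply is that the lead AE statistic is the number and percentage of subjects, which splitting cannot change. Protocol 10.9.2 specifies subject incidence, and SAP 12.0 rules out formal testing. That stands, and it limits the consequence to the event-count figures. Those figures are still planned outputs for the primary objective.

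A second reply is that the TEAE wording covers only first occurrence or increase, so step-down records are arguably excluded. That is a fair reading, but it still leaves three events for the episode in step 1, and it does not reach SAEs and AESIs.

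Third, solicited injection-site reactions have their own subject-level tables (SAP 12.6.2) and become AEs only if the investigator considers them adverse. This also stands and narrows the effect.

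A reader might infer more: that counts are inflated most in the most reactogenic arms. The documents do not support this. It needs AEs in those arms to change severity or relationship more often, and no rate is given. Suppose peak severities (mild/moderate/severe) of 80/15/5% in one arm and 50/30/20% in another, equal true event numbers, and step-ups only. If a share f of the non-mild events is recorded at every lower grade first, the relative inflation is (1 + 0.70f)/(1 + 0.25f). That is 1.04 at f = 0.10, 1.20 at f = 0.50, and 1.36 only if f = 1. The severity mixes and f are all assumed.

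On the outcome list, a reader might infer that a death could not be coded at all. The eCRF is not among the documents and may hold a fatal code, and deaths are captured as SAEs. Only the mismatch between the protocol list and the planned outputs is shown.

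**Conclusion.** The point holds for event counts. As written, SAP 12.6.1 allows one continuing AE to be counted as several events in the overall summary and in seven of the eight SOC and preferred-term tables. For SAEs and AESIs every split record would count, including those created by a decrease. Subject-level incidence is sound.

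The size cannot be determined from the documents. The worked episode gives three to five events instead of one, and the arm-level figures are illustrations on assumed inputs. The surplus can be larger in an arm whose AEs change grade more often. Whether any arm is like that is unknown, so no direction of bias between arms is established.

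The missing fatal category is a separate inconsistency between Protocol 9.2.3.2 and the planned outputs.

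**What to change.** In SAP 12.6.1:
- Link successive records of one continuing AE, preferably by an event identifier. Matching on preferred term and adjoining dates could merge distinct events.
- Count each episode once per table, at its maximum treatment-emergent severity and strongest relationship.
- Date it from its first treatment-emergent record, so that a pre-dose AE that worsens after dosing remains a TEAE.
- State that a record created only by a decrease is not a new event, and apply this to the SAE and AESI tables too.
- Compute any AE duration on the linked episode.
- Keep the split records in the listings.

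Separately, reconcile Protocol 9.2.3.2 with the fatal-outcome tables and listing, either by adding a fatal category or by naming the SAE field that feeds them.

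The cost is a short extra derivation, slightly lower event counts, and a line of text on outcome. The SAP changes fit the route in SAP 4.0, where the final version is issued after the blinded data review meeting and before database lock.

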9.2.3 Assessment of causality

Causal relationship assessment to drug treatments is required for purposes of reporting AEs. To promote consistency, the following guidelines should be taken into consideration along with good clinical and scientific judgment when determining the relationship of Vaccine FP-02.2 to an AE:

- Reasonable Possibility: a causal relationship with the IMP cannot be excluded
- No Reasonable Possibility: there is no reasonable evidence to suggest a causal relationship between Vaccine FP-02.2 and the AE.
- No Possibility: there is no possibility for a causal relationship. This assessment will likely only be applied to AEs recorded prior to administration of IMP.

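### The pre-dose benchmark in the TEAE rule is not limited to events ongoing at the first dose, so a new post-dose episode can be left out of the TEAE tables

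*SAP*

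**What the plan says.** SAP 12.6.1 defines TEAEs as "those which first occur or increase in severity or relationship probability to investigational product after the first dose of investigational product", up to 30 days after the last dose. An AE that changes in severity or relationship becomes a new record with a new start date.

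The benchmark rule follows. Its stated trigger is that a subject had two or more pre-dose AEs sharing a preferred term; the worst of these "will be used as the benchmark for comparison to the AEs occurring during the study under the preferred term". The unit of comparison is the preferred term, not the episode. Nothing is said about whether the pre-dose AE had resolved.

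The protocol does not define a TEAE, but two of its rules feed this one:

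- Section 9.2: "All AEs must be fully recorded throughout the entire study period (from Screening Visit to Day 85". Resolved pre-dose events are therefore in the data. Screening may start 28 days before dosing (section 7.2.1).
- Section 9.2.3 has three causality codes: *Reasonable Possibility*, *No Reasonable Possibility* and *No Possibility*. The last two both mean unrelated. Of *No Possibility* it says: "This assessment will likely only be applied to AEs recorded prior to administration of IMP". This is an expectation, so either code may be used before dosing.

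SAP 12.6.1 summarises all SAEs and AESIs whether or not they are treatment-emergent, and all AEs are listed.

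**The concern.** A comparison with a pre-dose state makes sense for an AE that carries across the first dose: has it worsened? It makes little sense for a headache that ended before dosing and a separate headache afterwards. The text does not distinguish the two cases.

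Unsolicited AEs to Day 85 are a primary endpoint (Protocol 3.3.1), and the by-arm summaries of non-serious AEs are TEAE tables (SAP Appendix 1, Tables 14.3.2.1 to 14.3.2.3). The study is first-in-man with 10 subjects planned per arm, so one subject is 10 percentage points. The events at risk are common and non-specific, and the blinded investigator judged them unrelated. All-causality tables exist so that the safety summary does not rest on that judgement.

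**Working it through.** **1. Which combinations drop out.** Order the codes *No Possibility* (NP) < *No Reasonable Possibility* (NRP) < *Reasonable Possibility* (RP). Under the literal rule a post-dose event is a TEAE if its severity or its code exceeds the benchmark's. There are 3 × 3 = 9 pairs of pre-dose and post-dose severity, and in 6 of them the post-dose event is no more severe. Pairs dropped, out of 9:

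| Benchmark code | Post-dose NP | Post-dose NRP | Post-dose RP |
|---|---|---|---|
| NP | 6 | 0 | 0 |
| NRP | 6 | 6 | 0 |

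A post-dose NRP event of equal or lower severity is kept in all 6 pairs if the benchmark was coded NP and dropped in all 6 if it was coded NRP. That is 6 changes of status among 9 × 3 = 27 combinations of severity pair and post-dose code. A post-dose RP event is never dropped when the benchmark carries a recorded unrelated code.

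**2. Example within the stated trigger.** A subject has a mild and a moderate headache in screening, both resolved, then a new moderate headache on Day 2 coded NRP. If both earlier events were coded NRP, the Day 2 event is not a TEAE. If both were coded NP, it is.

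If the mild one was NRP and the moderate one NP, the answer depends on whose code is used. It is a TEAE against the most severe event's code (NP), but not against the highest code (NRP). The SAP chooses the benchmark by severity only and does not settle this.

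**3. Size.** The plan has no figure to reproduce. Assumptions, for one preferred term:

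- Poisson onsets at rate r per 28 days and independent episodes.
- A 28-day pre-dose period.
- A window from Day 1 to 30 days after Day 57, which is 86 days, so λ = r × 86/28.
- Severity 70/25/5% mild/moderate/severe, with cumulative F = 0.70, 0.95, 1.
- The same unrelated code before and after dosing.

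For severity level k:

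- P(at least one pre-dose event, worst = k) = exp(−r(1−F_k)) − exp(−r(1−F_{k−1})), with F_0 = 0.
- For at least two pre-dose events, subtract r·exp(−r)·p_k, where p_k is the share at level k.
- P(at least one post-dose event, worst ≤ k) = exp(−λ(1−F_k)) − exp(−λ).
- Loss = sum over k of the pre-dose term times the post-dose term. Share lost = loss / (1 − exp(−λ)).

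For r = 0.3: λ = 0.9214 and 1 − exp(−λ) = 0.602.

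- Any pre-dose event: 0.1731 × 0.3605 + 0.0712 × 0.5570 + 0.0149 × 0.6020 = 0.111, and 0.111/0.602 = 18.4%.
- At least two: 0.0175 × 0.3605 + 0.0156 × 0.5570 + 0.0038 × 0.6020 = 0.0173, and 0.0173/0.602 = 2.9%.

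| r per 28 days | Share lost, more than one pre-dose AE | Share lost, one or more | Absolute loss (points), more than one | Absolute loss (points), one or more |
|---|---|---|---|---|
| 0.05 | 0.1% | 3.7% | 0.01 | 0.5 |
| 0.1 | 0.4% | 7.2% | 0.1 | 1.9 |
| 0.2 | 1.4% | 13.3% | 0.6 | 6.1 |
| 0.3 | 2.9% | 18.4% | 1.7 | 11.1 |

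Given the rates and severity mix, these are upper limits with respect to coding, because a rise in relationship category can only rescue an event. If every pre-dose AE is coded NP and post-dose AEs are NRP or RP, the loss is zero.

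**The case against.** The strongest reply is that the benchmark sentence is only a tie-breaker. It applies when more than one pre-dose AE shares a preferred term, and it says which one to use. A reader might infer that, on the literal text, a subject with one resolved pre-dose headache loses a later one. The sentence does not say so. A single event becomes the comparator only by implication, although a rule that suppressed repeats after two resolved events but not after one would be odd.

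A second reply is that a post-dose onset can be read as first occurring after the dose, and so is a TEAE at once. The comparison would then serve only AEs split into new records across the first dose, as the preceding sentence on changed AEs suggests. This reading is reasonable, but the SAP does not state it, and the comparison is written for on-study AEs under the term without exempting new episodes. Two programmers could derive different counts.

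Third, the exposure is narrow. SAEs and AESIs are exempt, injection site reactions have their own tables, the listings are complete, the rule is the same in every arm and no hypothesis is tested. All of this stands and limits the consequence.

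A reader might also infer that the relationship criterion is the fault and should be deleted. The documents do not support that. It is an alternative condition, so it can only add TEAEs. Without it, an AE ongoing at the first dose and later re-judged *Reasonable Possibility* at unchanged severity would leave the possibly-related TEAE table.

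**Conclusion.** The point holds as a defect of wording with a limited reach. The SAP does not require the pre-dose AE to be ongoing, so read literally it can exclude new post-dose episodes from the all-causality TEAE tables, and the pre-dose choice between two unrelated codes can decide the outcome.

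The loss per preferred term is about 0.1% to 2.9% of subjects with a post-dose event under the stated trigger, about 4% to 18% if one pre-dose AE is enough, and none if pre-dose AEs are uniformly coded *No Possibility* and post-dose AEs are not. These ranges rest on assumed rates, an assumed severity mix, identical coding and a full 28-day screening period.

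A reader might take from the upper end that about one subject in an arm of 10 would be lost. That needs the highest assumed rate, the implied single-event comparator and identical coding together; under the stated trigger the figure is 1.7 points. Nor do the documents support a reading that the rule hides events judged related: with a recorded unrelated code before dosing, those are always kept.

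**What to change.** In SAP 12.6.1:

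- State that any AE with onset after the first dose, within the existing window, is a TEAE, whether or not a resolved AE of the same preferred term occurred before.
- Apply the pre-dose benchmark only to records that continue an AE still ongoing at the first dose.
- Keep the relationship criterion for those ongoing AEs, but treat *No Possibility* and *No Reasonable Possibility* as one category, so that only a change to *Reasonable Possibility* counts as an increase. This also stops an unchanged ongoing AE from becoming a TEAE merely because it was re-coded from one unrelated code to the other.

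The cost is a few lines of SAP text and one derivation in the AE dataset, with no new data. The downside is slightly higher TEAE counts.
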